4.2.3 Analysis of Secondary Efficacy Variables

Secondary efficacy analyses will be conducted on the AUS ITT or PP populations as specified below.

Cholesterol Retesting

During the use period of the study, participants will be told through the Web App and transactional emails to retest their LDL-C within 3 months. Participants who should retest are those who were eligible for continuous treatment. The percentage of participants who are eligible for continuous treatment and have a cholesterol retest within 6 months of starting medication that was verified at Virtual Visit 2 will be calculated as follows:

$$\text{Percentage} = \frac{100 * (\text{Number of participants who are eligible for continuous treatment and had a cholesterol retest within 6 months after starting medication that was verified at Visit 2})}{\text{Total number of participants who are eligible for continuous treatment}}$$

The number and percentage of participants who are eligible for continuous treatment and have a cholesterol retest within 6 months of starting medication that was verified at Virtual Visit 2 will be summarized on the PP population overall and by subgroups. Those participants with an unverified cholesterol retest value at Visit 2, and thus required study mandated testing, will not be included in the numerator for this endpoint. Participants with multiple retests will be included in the numerator for this endpoint if at least one of the retests is a non-study mandated verified retest. That is, at least one of the retests has a Source Type equal to “Verified source” on the

Visit 2 Diagnostic Report. The total number of participants who are eligible for continuous treatment will serve as the denominator for the percentages.

The target threshold for this endpoint is that the observed PE needs to be at least 60% in the overall analysis. There are no target thresholds for the subgroup analyses.

An additional analysis of cholesterol retesting will be conducted on those participants in the AUS ITT population. The percentage of participants who had a cholesterol retest within 6 months of starting medication that was verified at Virtual Visit 2 will be calculated as follows:

$$\text{Percentage} = \frac{100^* \text{ (Number of participants who had a cholesterol retest within 6 months after starting medication that was verified at Visit 2)}}{\text{Total number of participants in the AUS ITT Population}}$$

The number and percentage of participants who had a cholesterol retest within 6 months of starting medication regardless of final use outcome that was verified at Virtual Visit 2 will be summarized on the AUS ITT population overall and by subgroups (Sensitivity Analysis #1). Those participants with an unverified cholesterol retest value at Visit 2, and thus required study mandated testing, will not be included in the numerator for this endpoint. Participants with multiple retests will be included in the numerator for this endpoint if at least one of the retests is a non-study mandated verified retest. That is, at least one of the retests has a Source Type equal to “Verified source” on the Visit 2 Diagnostic Report. The total number of participants in the AUS ITT population will serve as the denominator for the percentages. There are no target thresholds for this analysis. Another table will be produced with this information based on duration of time in the study (i.e., ≤ 2 months, ≤ 3 months, ≤ 4 months, ≤ 5 months, 6+ months).

An additional analysis to assess the percentage of participants who had a cholesterol retest within 6 months after starting medication that was verified at Visit 2 in the population of participants that reordered medication at least once will be conducted and summarized on the AUS ITT population overall and by subgroups (Sensitivity Analysis #2).

Lastly, an analysis to assess the percentage of participants who had a cholesterol retest within 6 months after starting medication that was verified at Visit 2 in those participants in the AUS ITT population who received at least 3 months of treatment will be conducted and summarized overall and by subgroups (Sensitivity Analysis #3).

Compliance with Stop Use Warning

The percentage of participants who correctly self-identify as having a “Stop Use” warning and stop medication will be calculated as follows:

$$\text{Percentage} = \frac{100^* \text{ (Number of participants who correctly self-identify as having a "Stop Use" warning and stop medication)}}{\text{Total number of participants who CMOG identify as having a "Stop Use" warning}}$$

The number and percentage of participants who correctly self-identify as having a “Stop Use” warning and stop medication will be summarized on the PP population overall and by subgroups.

Compliance with Do Not Use Warning

The percentage of participants who correctly self-identify as having a “Do Not Use” warning at the final use assessment will be calculated as follows:

$$\text{Percentage} = \frac{100^* \text{ (Number of participants who correctly self-identify as having a "Do Not Use" warning at the final use assessment)}}{\text{Total number of participants who CMOG identify as having a "Do Not Use" warning}}$$

The number and percentage of participants who correctly self-identify as having a “Do Not Use” warning at the final use assessment will be summarized on the PP population overall and by subgroups.

Compliance with Ask a Doctor Before Use Warning

The percentage of participants who correctly self-identify as having an “Ask a Doctor Before Use” warning at the final use assessment will be calculated as follows:

$$\text{Percentage} = \frac{100^* \text{ (Number of participants who correctly self-identify as having an "Ask a Doctor Before Use" warning at the final use assessment)}}{\text{Total number of participants who CMOG identify as having an "Ask a Doctor Before Use" warning}}$$

The number and percentage of participants who correctly self-identify as having an “Ask a Doctor Before Use” warning at the final use assessment will be summarized on the PP population overall and by subgroups.

Compliance with Continuous Dosing

Compliance will be assessed in three ways, using pill counts, the eDiary and the number of reorders. The data from these three methods should provide a robust assessment of compliance in this study.

Overall Compliance will be calculated for each participant using pill counts as follows:

Overall Compliance =	$\frac{100^* \text{ (Total Number of Pills Taken)}}{\text{Intended Duration (in days) of Treatment}}$
-------------------------	---

The intended duration of treatment is defined in [Section 3.2.10](#).

If a situation occurs in which a participant returns fewer bottles than ordered, the convention for counting pills taken (i.e., the numerator for Overall Compliance) will be to take the total number of pills taken during the use period of the study using the electronic data capture (EDC) drug accountability data and the eDiary data to determine the number of pills taken during the supply period corresponding to the missing bottle(s).

Each participant will have overall compliance assessed and will be considered successfully compliant with continuous dosing if overall compliance is between 50% and 120%. The target threshold for the overall compliance endpoint is that the observed point estimate for the percentage of participants falling in the 50-120% range needs to be at least 50% overall. That is, at least half of the participants need to be successfully compliant with continuous dosing. A lower bound of 50% was chosen because published clinical studies have reported intermittent dosing with as little as 5 mg to 10 mg once weekly can provide significant reductions in LDL-C^{3,4,5,6,7}.

Overall Compliance will be summarized using descriptive statistics on the PP population overall and by subgroups.

The number and percentage of participants with >0-<50%, 50-120% and >120% overall compliance will be summarized on the PP population overall and by subgroups.

A Longitudinal Compliance Rate will be calculated to assess compliance with continuous dosing across each study drug reorder supply period. In order to derive the longitudinal compliance rate, supply period compliance will first be calculated for each supply period for each participant as follows:

Supply Period Compliance =	$\frac{100^* \text{ (Total Number of Pills Taken in Supply Period } i \text{ based on the eDiary)}}{}$
-------------------------------	--

Intended Duration (in days) of Treatment in Supply Period i
--

The intended duration of treatment in supply period *i* is defined in [Section 3.2.11](#).

Missing e-diary entries will be treated as missed dosing.

Each participant will be considered successfully compliant across all supply periods if each supply period compliance is between 50% and 120%. The Longitudinal Compliance Rate will then be assessed as:

$$\text{Longitudinal Compliance Rate (\%)} = \frac{100^* (\text{Number of participants with 50-120\% Supply Period Compliance across all supply periods})}{\text{Total number of participants in PP population for whom supply period compliance was assessed across all supply periods}}$$

The target threshold for the Longitudinal Compliance Rate endpoint is that the observed point estimate needs to be at least 50% overall. That is, at least half of the participants need to be successfully compliant with continuous dosing across all supply periods.

Longitudinal Compliance Rate, along with the number of participants with 50-120% supply period compliance across all supply periods, will be summarized on the PP population overall and by subgroups.

An additional assessment of longitudinal compliance will be performed using reorder data from the Web App. Percentage of participants who were persistent as determined by reorder data from the Web App will be calculated as follows:

$$\text{Percentage} = \frac{100^* (\text{Number of participants who were persistent})}{\text{Total number of participants eligible for continuous treatment}}$$

Persistence is defined as participants eligible for continuous treatment and delivered the full 180 days or more of treatment. The number and percentage of participants who were persistent will be summarized on the PP population and AUS ITT population overall and by subgroups.

The target threshold for this endpoint is that the observed point estimate needs to be at least 50% overall.

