3.2.10 Pill Count

At Virtual Visit 2, all administered pill bottles will be returned, and pill count will be assessed. The total number of pills dispensed is based on the number of 45-day or 90-day supplies ordered through the Web App. The number of pills returned is the total number of pills remaining in each of the returned bottles. For those participants who refuse to send back their pill bottles for a final pill count, the option to count the pills with the study personnel via video conference will be given. For those participants who have lost one or more of their pill bottles, the eDiary data will be utilized to reconcile compliance with dosing.

Because there may be instances in which a participant continues study medication when they should not have (i.e., participant experiences “Stop Use,” “Do Not Use,” or “Ask a Doctor” warning) but does not stop medication, in order to properly assess compliance with continuous dosing, the intended duration of treatment will be used rather than the actual duration of treatment. The intended duration of treatment is as follows:

Intended Duration of Treatment =	(Intended Treatment Stop Date – Date Participant Received First Supply of Study Drug) + 1 Day
----------------------------------	---

where the date of intended treatment stop will be the date when the medication was intended to be stopped (i.e., the date of “Stop Use” warning, the date of the “Do Not Use” warning, the date of the “Ask a Doctor” warning in situations where the participant did not confirm the doctor gave them permission to use the drug, the date of discontinuation or withdrawal, or for participants who did not receive one of the previous outcomes, the date of Visit 2).

Data listings will be provided for participants TASS initial study drug order and their overall study drug accountability.

3.2.11 eDiary

The eDiary will be used to gather minimal and unbiased data on the participant's use of the IP. The information to be gathered will include dosing (date/time and amount of IP taken), adverse

events (changes in health), and medication changes. The participant will record the unique ID from the study drug bottle to confirm receipt of the product.

At the 60-day and 120-day planned telephone contacts, the eDiary will be reviewed to determine if “Stop Use” criteria may be present and to ask about any changes in health.

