In assessing supply period compliance, the total number of pills dispensed in supply period i will be either 45 or 90 based on the supply ordered and the total number of pills taken is determined based on the information recorded in the eDiary. The start date for assessing compliance in the eDiary will be the first day that the participant records taking the medication. From the start date, supply periods for evaluation of the eDiary are calculated based on the supply ordered. Therefore, the first supply period will include next 45 days for a 45-day supply and the next 90 days for a 90-day supply. The next supply period will start immediately after the first supply period ends, and the duration is based on supply. This method for determining the dates in the eDiary that are assessed for dosing relative to the supply periods will continue until the subject completes Virtual Visit 2 or has an event for which early stopping of therapy is required. In other words, the duration of treatment in the supply period for evaluation in the eDiary can be less than 45 or 90 days in those situations where the participant experiences an event that requires stopping therapy. Thus, the intended duration of treatment for supply period i will be calculated as follows:

Intended Duration of Treatment in Supply Period i =	(Intended Treatment Stop Date in Supply Period i – Date Participant Received First Supply of Study Drug in Supply Period i) + 1 Day
--	--

where the date of intended treatment stop in supply period i will be the date when the entire supply of medication was intended to be used by the participant (assuming one tablet is taken per day) or when the medication was intended to be stopped (i.e., the end date of intended supply period based on number of pills ordered, the date of “Stop Use” warning, the date of “Do Not Use” warning, the date of discontinuation or withdrawal).

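### The eDiary Longitudinal Compliance Rate rests on conflicting start-date, missing-entry and denominator rules, so participants who never record a dose can drop out of a rate judged against 50%

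*SAP*

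**What the plan says.** Four rules in the SAP bear on the eDiary measure.

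- **Denominator (SAP 4.2.3; same in Protocol 9.4.2.2):** "Total number of participants in PP population for whom supply period compliance was assessed across all supply periods". Neither document says what makes a participant assessed or not assessed.
- **Start of the window (SAP 3.2.11):** "The start date for assessing compliance in the eDiary will be the first day that the participant records taking the medication". Supply periods of 45 or 90 days are then laid end to end from that day.
- **Duration formula (also SAP 3.2.11):** the intended duration in a supply period is counted from the "Date Participant Received First Supply of Study Drug in Supply Period" concerned, that is, from receipt and not from first use.
- **Missing entries (SAP 4.2.3):** "Missing e-diary entries will be treated as missed dosing".

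A participant succeeds if every supply period lies between 50% and 120%. The endpoint succeeds if the observed proportion is at least 50%, with no confidence bound. The SAP explains this target as at least half of the participants.

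For the separate pill-count measure, SAP 4.2.3 assesses overall compliance for each participant and plans this display: "The number and percentage of participants with >0-<50%, 50-120% and >120% overall compliance will be summarized on the PP population".

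**The concern.** Two programmers could follow the SAP faithfully and produce different rates. One takes the start-date rule literally: no recorded dose means no start date, no supply period and nothing to assess, so the participant leaves the denominator. The other takes the missed-dose rule literally: an empty diary is 0% and the participant is a failure.

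Such participants can be in PP. Membership requires delivery of study drug plus Virtual Visit 2 or enough history to determine a final use outcome. It does not require any dosing or diary use.

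The start-date rule also leaves the days between delivery and first recorded dose outside the window, although on the missed-dose rule those days are misses. What is at stake is whether a secondary endpoint with a preset threshold is declared met.

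**Working it through.** **The plan's own figure.** No expected rate, sample size or power is stated for the compliance endpoints, so there is nothing to reproduce for this measure. For scale I take N = 500, the minimum planned for the second co-primary endpoint, which is analysed on PP.

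**Inputs.** N = 500 (SAP 1.3). Threshold 50%, point estimate only (SAP 4.2.3). k = PP participants with no recorded dose; the documents do not give it, and I assume 5 to 100 (1% to 20% of PP).

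**Step 1: lowest full-PP rate that still passes.** If the k non-recorders are dropped, the number of successes needed is 0.5 × (500 − k), rounded up. Dividing by 500 expresses it as a share of all PP participants.

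| k dropped | Denominator used | Successes needed | As share of all 500 |
|---|---|---|---|
| 0 | 500 | 250 | 50.0% |
| 5 | 495 | 248 | 49.6% |
| 10 | 490 | 245 | 49.0% |
| 25 | 475 | 238 | 47.6% |
| 50 | 450 | 225 | 45.0% |
| 75 | 425 | 213 | 42.6% |
| 100 | 400 | 200 | 40.0% |

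**Step 2: the same effect from the other side.** Reported rate = full-PP rate × 500/(500 − k). With 225 successes (45.0% of PP), the reported rate is 225/475 = 47.4% at k = 25, 225/450 = 50.0% at k = 50, and 225/400 = 56.25% at k = 100.

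**Step 3: direction.** Everyone dropped this way would be a failure under the missed-dose rule. The numerator is unchanged and the denominator shrinks, so the rate rises for any k above zero and at least one success.

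**Step 4: late starters.** This effect does not need any non-recorders. As an assumed example, take a 45-day supply with the first recorded dose on day 31 after delivery, then two doses in every three days.

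- Window from first recorded dose: 45 days, 30 doses, 30/45 = 67%, compliant.
- Window from delivery: only days 31 to 45 carry doses, 10 doses, 10/45 = 22%, not compliant.

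The days left out contain no recorded dose by construction, so leaving them out removes only misses. Moving the start also moves later period boundaries, which could shift an individual either way. I therefore do not put a size on this second effect.

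**Step 5: pill count.** Overall compliance is pills taken divided by intended duration. A participant who took none has 0 divided by a positive number of days, which is 0%. That participant is assessed, stays in PP and fails the 50–120% test. The rate does not change.

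**The case against.** **The exclusion is inferred, not stated.** No sentence removes non-recorders. The duration formula starts at receipt, so it needs no recorded dose. SAP 4.2.3 also says supply period compliance is calculated for each participant. Read that way, a non-recorder is computed as 0% and fails. This stands as far as it goes: it shows that a harmless reading exists, not that it governs. The start-date sentence is equally explicit and points the other way.

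**k may be small.** Unwillingness to complete the eDiary is an exclusion criterion (Protocol 5.3). More than seven days of diary inactivity triggers staff contact (Protocol 8.1). Diaries are reviewed at days 60 and 120 and at Virtual Visit 2, and refusing the diary can lead to withdrawal (Protocol 7.2). These safeguards make the upper end of my range less likely; at k = 5 the shift is 0.4 points. They are operational measures, however, and do not settle the analysis rule.

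**Upward relative to what?** Some non-recorders may have taken the drug. The shift is upward relative to the SAP's missed-dose convention; bias relative to actual dosing is not shown.

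**A tempting stronger reading** is that the pill-count measure also drops non-users, because its bands start above 0%. The documents do not support this. Each participant is assessed and the summary is on PP, so a missing 0% band is a gap in a table, not an exclusion. Participants who return all their pills are removed from the Safety population only. The missed-dose rule concerns diary entries; it reaches the pill count only where bottles are missing: "For those participants who have lost one or more of their pill bottles, the eDiary data will be utilized to reconcile compliance with dosing".

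**Limited consequence.** This is one of three secondary compliance measures, and Protocol 3.1 regards LDL-C lowering and reordering as the best indicators. That bears on priority, not on whether the rules conflict.

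**Conclusion.** The point holds for the eDiary Longitudinal Compliance Rate. Its start-date, duration, missing-entry and denominator rules do not fit together, and one faithful reading removes participants whom another counts as failures. The removal can only raise the rate relative to the missed-dose rule. The size depends wholly on k: from 0.4 points of slack at the threshold (k = 5) to 10 points (k = 100), with N = 500 assumed for PP. It would decide the endpoint only if the full-PP rate fell in that range just below 50%.

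A reader should not infer that the SAP certainly excludes non-recorders, nor that both dosing measures are biased. The first is a possible reading of undefined wording; the second fails on the text for the pill count. The conflict is worth resolving because the threshold has no margin and the correction is cheap.

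**What to change.** In SAP 3.2.11 and 4.2.3 and Protocol 9.4.2.2:

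- Make all PP participants the denominator of the Longitudinal Compliance Rate, and delete or define the condition about being assessed.
- State that a participant with no recorded eDiary dose is non-compliant.
- Start supply period 1 at the delivery date, as the SAP's own formula does. Every PP participant has had drug delivered, so everyone then has a first period. Let later periods follow on consecutively, as the SAP text already has them, and word the formula to match.

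As a minor tidy-up, change the lowest overall-compliance band to 0–<50% in SAP 4.2.3 and in the LDL-C-by-compliance summary in 4.2.4, so that a 0% participant has a row.

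**Cost.** Wording and programming only; no new data. Participants who took drug but ignored the diary will count as failures. The missed-dose rule already implies that, and the pill count shows their dosing separately.

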4.2.4 Analysis of Exploratory Efficacy Variables

Exploratory efficacy analyses will be conducted on the PP population unless otherwise specified.

Incorrect TASS Entries

For the initial TASS assessment, the number and percentage of incorrect TASS entries entered into the TASS tool by the participant, along with the reasons for incorrect TASS entries, will be summarized for each TASS question on the SS population overall and by subgroups. Additionally, data listings will be provided for reasons for incorrect participant TASS entries at the initial TASS assessment, and the central assessor discrepancy probes at Visit 1. A similar evaluation will be made on the final use assessment entries in the SS population.

There may be instances when a participant will be required to have a study mandated test at Visit 1, or at final use visit. For example, the LDL-C value entered by the participant may not be verified at Visit 1. The number and percentage of participants requiring a SMT will be analyzed overall and by subgroup for laboratory tests and blood pressure at Visit 1 and for LDL-C at the Final Use Visit.

Descriptive statistics will be provided for the absolute difference between the laboratory and BP data that was unable to be verified at Virtual Visit 1 but was entered into the TASS tool by the participant and the laboratory and BP data resulting from study mandated testing and entered into the TASS tool by the CMOG. These data will be summarized on the SS population overall and by subgroups.

Additionally, the number and percentage of laboratory or BP TASS entries between the participant and CMOG with absolute value of the relative differences that are $\leq 1x$, $>1x$ to $\leq 2x$, $>2x$ to $\leq 3x$, $>3x$ to $\leq 4x$, $>4x$ to $\leq 5x$ and $>5x$ the variability for each parameter as defined in the Laboratory and Blood Pressure Variability Assessments section of the Appendix will be summarized on the SS population overall and by subgroups.

Variability in the absolute difference in 10-year ASCVD risk scores calculated in the TASS tool based on the participant and CMOG entries will be summarized on the SS population overall and by subgroups. The intraclass correlation coefficient (ICC) (Watson and Petrie, 2010)⁹ will be computed to evaluate the agreement between these two scores on the population SS overall and by subgroups. Bland-Altman plots will be generated to show the difference in risk scores on the y-axis and the mean of the risk scores on the x-axis (Altman and Bland, 1983)⁸ on the SS population overall and by subgroups. A scatterplot will be constructed using the ASCVD risk scores calculated in the TASS tool based on the entries made by the participant and those made by the CMOG on the SS population overall and by subgroups. Lin's concordance correlation coefficient (Lin, 1989)¹⁰ will be calculated between the two ASCVD risk scores on the SS population overall and by subgroups.

For the initial participant TASS assessment, the number and percentage of incorrect TASS entries entered into the TASS tool by the participant will be summarized for each TASS question along with the number and percentage of incorrect TASS entries that resulted in incorrect outcomes. The number and percentage of incorrect TASS entries that resulted in incorrect TASS outcomes that could be mitigated *a priori* and post-study will also be summarized. This information will be summarized in the SS population overall and by subgroups. A similar evaluation will be made on the final participant TASS assessment entries in the PP population overall and by subgroups. Mitigations are further assessed based on whether the mitigation was performed *a priori* or post-study for the initial participant TASS assessment in the SS population overall and by subgroups and repeated using the AUS ITT population and PP population. A similar evaluation will be conducted for the final participant TASS assessment in the PP population overall and by subgroups.

An exploratory analysis of the number and percentage of participants with incorrect TASS entries which could be mitigated, regardless of whether the entry impacted the first or second co-primary endpoint, will be summarized for each TASS question on the SS, AUS ITT and PP populations overall and by subgroups for the initial assessment and the PP population overall and by subgroup for the final use assessment. Data listings will be provided to explore the initial and final assessments between the participant and CMOG TASS inputs with applied mitigations, regardless of the impact on the first co-primary endpoint, for the SS populations.

The number and percentage of participants with incorrect TASS entries into the TASS tool, along with the reasons for incorrect TASS entries, during the initial assessment will be summarized for each TASS question on the SS population overall and by subgroups. The number and percentage of participants with incorrect TASS entries, along with the reasons for incorrect TASS entries, at the final use assessment will be summarized for each TASS question on the PP population overall and by subgroups. A data listing will be provided for reasons for incorrect TASS entries at the final TASS assessment.

Discrepancies between TASS entries by the participant and participant responses to the same questions asked by the CMOG and recorded on the medical and medication history form will be summarized overall and by subgroups for the SS population at Visit 1 and for the SS population at the final use visit.

Compliance with Speak to a Doctor Component of Stop Use Warning

The percentage of participants who correctly self-identify as having a “Stop Use” warning and speak to a doctor will be calculated as follows:

$$\text{Percentage} = \frac{100 * (\text{Number of participants who correctly self-identify as having a “Stop Use” warning and speak to a doctor})}{\text{Total number of participants who correctly self-identify as having a “Stop Use” warning}}$$

The number and percentage of participants who correctly self-identify as having a “Stop Use” warning and speak to a doctor will be summarized on the PP population overall and by subgroups.

Timeframe for Complying with Stop Use Warning

As discussed in [Section 3.2.6](#), the data for assessing the Stop Use timeframe will come from the Targeted Medical and Medication History Form at Visit 2. For those participants who correctly self-identify as having a “Stop Use” warning and stop the medication, the date from when a participant identifies a “Stop Use” warning to the date the medication was stopped will be calculated, in number of days, as follows:

$$\text{Time from having a “Stop Use” warning to stopping the medication (in days)} = (\text{Date medication was stopped} - \text{Date of “Stop Use” warning}) + 1 \text{ Day}$$

Descriptive statistics for time (in days) from having a “Stop Use” warning to stopping the medication will be summarized on the PP population overall and by subgroups.

For those participants who correctly self-identify as having a “Stop Use” warning and contact a doctor, the date from when a participant identifies a “Stop Use” warning to the date their doctor was contacted will be calculated, in number of days, as follows:

$$\text{Time from having a “Stop Use” warning to contacting a doctor (in days)} = (\text{Date doctor contacted} - \text{Date of “Stop Use” warning}) + 1 \text{ Day}$$

Descriptive statistics for time (in days) from having a “Stop Use” warning to contacting a doctor will be summarized on the PP population overall and by subgroups.

Timeframe for Complying with Do Not Use Warning

As discussed in [Section 3.2.7](#), the data for assessing the “Do Not Use” timeframe will come from the Targeted Medical and Medication History Form at Visit 2. For those participants who correctly self-identify as having a “Do Not Use” warning and stop the medication, the date from when a participant identifies a “Do Not Use” warning to the date the medication was stopped will be calculated, in number of days, as follows:

$$\text{Time from having a “Do Not Use” warning to stopping the medication (in days)} = \frac{\text{(Date medication was stopped – Date of “Do Not Use” warning)}}{+ 1 \text{ Day}}$$

Descriptive statistics for time (in days) from having a “Do Not Use” warning and stopping the medication will be summarized on the PP population overall and by subgroups.

Compliance with Speak to a Doctor Component of Ask a Doctor Before Use Warning

The percentage of participants who correctly self-identify as having an “Ask a Doctor Before Use” warning and speak to a doctor will be calculated as follows:

$$\text{Percentage} = \frac{100 * (\text{Number of participants who correctly self-identify as having an “Ask a Doctor Before Use” warning and speak to a doctor})}{\text{Total number of participants who correctly self-identify as having a “Ask a Doctor Before Use” warning}}$$

The number and percentage of participants who correctly self-identify as having a “Ask a Doctor Before Use” warning and speak to a doctor will be summarized on the PP population overall and by subgroups.

Timeframe for Complying with Ask a Doctor Before Use Warning

As discussed in [Section 3.2.8](#), the data for assessing the Ask a Doctor timeframe will come from the Targeted Medical and Medication History Form at Visit 2. For those participants who correctly self-identify as having an “Ask a Doctor Before Use” warning and contact a doctor, the date from when a participant identifies an “Ask a Doctor Before Use” warning to the date their doctor was contacted will be calculated, in number of days, as follows:

$$\text{Time from having a “Ask a Doctor Before Use” warning to contacting a doctor (in days)} = \frac{\text{(Date doctor contacted – Date of “Ask a Doctor Before Use” warning)}}{+ 1 \text{ Day}}$$

Descriptive statistics for time (in days) from having a “Ask a Doctor Before Use” warning and contacting a doctor will be summarized on the PP population overall and by subgroups.

Evaluations of Effectiveness in Lowering LDL-C in Different Participant Subgroups

For participants determined to be eligible for continuous treatment at Visit 2, the difference in PCFB in LDL-C between participants who had a retest LDL-C value during the course of the study with a verified source and those who did not retest but had a SMT completed at Virtual Visit 2 will be assessed. PCFB will be calculated for each of these participant subgroups in the same manner as the primary LDL-C endpoint. The absolute difference in PCFB between these two subgroups will be calculated and descriptive statistics will be summarized on the PP and AUS ITT population overall and by subgroups.

Evaluation of LDL-C Lowering Relative to Level of Dosing Compliance

Descriptive statistics for PCFB in verified LDL-C at Visit 2 for those participants eligible for continuous treatment will be summarized by level of overall compliance (>0 - <50%, 50-120%, and >120%) in the PP population overall and by subgroups, and for those participants with supply period compliance between 50% and 120% across all supply periods, in the PP population overall and by subgroups. The calculations for overall compliance and supply period compliance will be calculated using the same method as previously described in [Section 4.2.3](#).

